5.7 Diet/Activity/Other Considerations

5.7.1 Diet

Subjects should maintain a normal diet unless modifications are required to manage an AE such as diarrhea, nausea or vomiting.

5.7.2 Contraception

Pembrolizumab and/or ipilimumab may have adverse effects on a fetus *in utero*. Furthermore, it is not known if pembrolizumab or ipilimumab have transient adverse effects on the composition of sperm. Non-pregnant, non-breast-feeding women may be enrolled if they are willing to use 2 methods of birth control or are considered highly unlikely to conceive. Highly unlikely to conceive is defined as 1) surgically sterilized, or 2) postmenopausal (a woman who is ≥45 years of age and has not had menses for greater than 1 year will be considered postmenopausal), or 3) not heterosexually active for the duration of the study. The two birth control methods can be either two barrier methods or a barrier method plus a hormonal method to prevent pregnancy. Subjects should start using birth control from study Visit 1 throughout the study period up to 120 days after the last dose of study therapy.

The following are considered adequate barrier methods of contraception: diaphragm, condom (by the partner), copper intrauterine device, sponge, or spermicide. Appropriate hormonal contraceptives will include any registered and marketed contraceptive agent that contains an estrogen and/or a progestational agent (including oral, subcutaneous, intrauterine, or intramuscular agents).

Subjects should be informed that taking the study medication may involve unknown risks to the fetus (unborn baby) if pregnancy were to occur during the study. In order to participate in the study they must adhere to the contraception requirement (described above) for the duration of the study and during the follow-up period defined in section 7.2.2-Reporting of Pregnancy and Lactation to the Principal Investigator. If there is any question that a subject will not reliably comply with the requirements for contraception, that subject should not be entered into the study.

5.7.3 Use in Pregnancy

If a subject inadvertently becomes pregnant while on treatment with pembrolizumab and/or ipilimumab, the subject will immediately be removed from the study. The site will contact the subject at least monthly and document the subject's status until the pregnancy has been completed or terminated. The outcome of the pregnancy will be reported to the Principal Investigator and to Merck without delay and within 24 hours to the Principal Investigator and within 2 working days to Merck if the outcome is a serious adverse experience (e.g., death, abortion, congenital anomaly, or other disabling or life-threatening complication to the mother or newborn).

The study investigator will make every effort to obtain permission to follow the outcome of the pregnancy and report the condition of the fetus or newborn to the Principal Investigator. If a male subject impregnates his female partner the study personnel at the site must be informed immediately and the pregnancy reported to the Principal Investigator and to Merck and followed as described above and in Section 7.2.2.

5.7.4 Use in Nursing Women

It is unknown whether pembrolizumab and/or ipilimumab is excreted in human milk. Since many drugs are excreted in human milk, and because of the potential for serious adverse reactions in the nursing infant, subjects who are breast-feeding are not eligible for enrollment.

5.8 Subject Withdrawal/Discontinuation Criteria

Subjects may withdraw consent at any time for any reason or be dropped from the trial at the discretion of the investigator should any untoward effect occur. In addition, a subject may be withdrawn by the investigator or the Principal Investigator if enrollment into the trial is inappropriate, the trial plan is violated, or for administrative and/or other safety reasons. Specific details regarding discontinuation or withdrawal are provided in Section 7.1.4 – Other Procedures.

A subject must be discontinued from the trial for any of the following reasons:

- The subject or legal representative (such as a parent or legal guardian) withdraws consent.
- Confirmed radiographic disease progression

Note: A subject may be granted an exception to continue on treatment with confirmed radiographic progression if clinically stable or clinically improved. Such cases should be discussed by the treating physician with the Principal Investigator.

- Unacceptable adverse experiences as described in Section 5.2.1.2
- Intercurrent illness that prevents further administration of treatment
- Investigator's decision to withdraw the subject
- The subject has a confirmed positive serum pregnancy test
- Noncompliance with trial treatment or procedure requirements
- The subject is lost to follow-up
- Completed 24 months of uninterrupted treatment with pembrolizumab or 35 administrations of study medication (which includes both doses of pembrolizumab and ipilimumab together for 4 doses followed by pembrolizumab monotherapy), whichever is later.

Note: 24 months of study medication is calculated from the date of first dose. Subjects who stop pembrolizumab after 24 months may be eligible for up to one year of additional study treatment if they progress after stopping study treatment provided they meet protocol requirements.

Administrative reasons

After the end of treatment, each subject will be followed for 30 days for adverse event monitoring. Subjects who discontinue for reasons other than progressive disease will have post-treatment follow-up for disease status until disease progression, initiating a non-study cancer treatment, withdrawing consent or becoming lost to follow-up. After documented disease progression each subject will be followed by telephone until death, initiating subsequent treatment, withdrawal of consent, or the end of the study, whichever occurs first.

5.8.1 Discontinuation of Study Therapy after CR

Discontinuation of treatment may be considered for subjects who have attained a confirmed CR that have been treated for at least 24 weeks with pembrolizumab and had at least two treatments with pembrolizumab beyond the date when the initial CR was declared. Subjects who then experience radiographic disease progression may be eligible for up to one year of additional treatment with pembrolizumab via the Second Course Phase at the discretion of the investigator if no cancer treatment was administered since the last dose of pembrolizumab, the subject meets the safety parameters listed in the Inclusion/Exclusion criteria, and the trial is open. Subjects will resume therapy at the same dose and schedule at the time of initial discontinuation. Additional details are provided in Section 7.1.4.2.

5.9 Clinical Criteria for Early Trial Termination

Early trial termination will be the result of the criteria specified below:

- 1. Quality or quantity of data recording is inaccurate or incomplete
- 2. Poor adherence to protocol and regulatory requirements
- 3. Incidence or severity of adverse drug reaction in this or other studies indicates a potential health hazard to subjects
- 4. Plans to modify or discontinue the development of the study drug

In the event of Merck decision to no longer supply study drug, ample notification will be provided so that appropriate adjustments to subject treatment can be made.

6.0 TRIAL FLOW CHART

6.1 Study Flow Chart

Trial Period:	Screenir	ng Phase	Treatment Cycles ^a						End of Treatment	Po	st-Treatment		
	Pre-	Main Study					To b	e repeat	ted beyone	ond 8			
Treatment Cycle/Title:	screening (Visit 1)	Screening (Visit 2)	1	2	3	4*	5	6	7	8	Discon	Safety Follow-up	
Scheduling Window (Days):		-28 to -1		± 3	± 3	± 3	± 3	± 3	± 3	± 3	At time of Discon	30 days post discon	Follow Up Visits ^b Every 12 weeks post discon
Administrative Procedures				-				-	-				
Informed Consent	X												
Inclusion/Exclusion Criteria		X											
Demographics and Medical History		X											
Prior and Concomitant Medication Review		X	X	X	X	X	X	X	X	X	X	X	X
Trial Treatment Administration		X	X	X	X	X	X	X	X	X			
Clinical Procedures/Assessments							•						
Review Adverse Events		X	X	X	X	X	X	X	X	X	X	X	X
Physical Examination		X	X	X	X	X	X	X	X	X	X	X	X
Vital Signs and Weight		X	X	X	X	X	X	X	X	X	X	X	X
ECOG Performance Status		X	X	X	X	X	X	X	X	X	X	X	X
Laboratory Procedures/Assessments: anal	ysis perforn	ned by LOC	AL lab	orator	y								
Pregnancy Test – Urine or Serum β-HCG		X											
CBC with Differential		X	X	X	X	X	X	X	X	X	X	X	
Comprehensive Serum Chemistry Panel		X	X	X	X	X	X	X	X	X	X	X	_
Urinalysis		X											
TSH (with reflexive T3, FT4 as indicated)		X	X	X	X	X	X	X	X	X	X	X	
Efficacy Measurements							•						

Trial Period:	Screenin	g Phase	Treatment Cycles ^a							End of Treatment	Po	st-Treatment	
	Pre-	Main Study					To be repeated beyond 8 cycles						
Treatment Cycle/Title:	screening (Visit 1)	Screening (Visit 2)	1	2	3	4*	5	6	7	8	Discon	Safety Follow-up	
Scheduling Window (Days):		-28 to -1		± 3	± 3	± 3	± 3	± 3	± 3	± 3	At time of Discon	30 days post discon	Follow Up Visits ^b Every 12 weeks post discon
Tumor Imaging (window includes all of cycle following drug administration)		X				X				X			
Tumor Biopsies/Archival Tissue Collection	n/Correlativ	e Studies Bl	ood										
Archival or Newly Obtained Tissue Collection ^C		X											
Correlative Studies Blood Collection ^C		X	X			X					X		
Fecal Sample		X				X							

a – Treatment cycles; *Treatment cycle 4 visit-to allow for the scan any time after infusion of the 4th dose.

b – Follow up visits for up to 2 years following drug discontinuation

c – Samples to be collected for correlative blood analysis are detailed in section 8.1.1.11

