Hyperthyroidism	3	Toxicity resolves to Grade 0-1	Toxicity does not resolve within 12 weeks of last dose or inability to reduce corticosteroid to 10 mg or less of prednisone or equivalent per day within 12 weeks.			
	4	Permanently discontinue both pembrolizumab and ipilimumab	Permanently discontinue both pembrolizumab and ipilimumab			
Hypothyroidism	2-4	Therapy with pembrolizumab can be continued while treatment for the thyroid disorder is instituted	Therapy with pembrolizumab and ipilimumab can be continued while treatment for the thyroid disorder is instituted.			
Infusion Reaction	3-4	Permanently discontinue both pembrolizumab and ipilimumab	Permanently discontinue both pembrolizumab and ipilimumab			
Pneumonitis	2	Toxicity resolves to Grade 0-1	Toxicity does not resolve within 12 weeks of last dose or inability to reduce corticosteroid to 10 mg or less of prednisone or equivalent per day within 12 weeks.			
	3-4	Permanently discontinue both pembrolizumab and ipilimumab	Permanently discontinue both pembrolizumab and ipilimumab			
Renal Failure or 2		Toxicity resolves to Grade 0-1	Toxicity does not resolve within 12 weeks of last dose or inability to reduce corticosteroid to 10 mg or less of prednisone or equivalent per day within 12 weeks.			
Nephritis	3-4	Permanently discontinue both pembrolizumab and ipilimumab	Permanently discontinue both pembrolizumab and ipilimumab			
All Other Drug- Related Toxicity ²	3 or Severe	Toxicity resolves to Grade 0-1	Toxicity does not resolve within 12 weeks of last dose or inability to reduce corticosteroid to 10 mg or less of prednisone or equivalent per day within 12 weeks.			
Aciaica Toxicity	4	Permanently discontinue both pembrolizumab and ipilimumab	Permanently discontinue both pembrolizumab and ipilimumab			

Note: Permanently discontinue for any severe or Grade 3 drug-related AE that recurs or any life-threatening event.

1 For patients with liver metastasis who begin treatment with Grade 2 AST or ALT, if AST or ALT increases by greater than or equal to 50% relative to baseline and lasts for at least 1 week then patients should be discontinued.

² Patients with intolerable or persistent Grade 2 drug-related AE may hold study medication at physician discretion. Permanently discontinue study drug for persistent Grade 2 adverse reactions for which treatment with study drug has been held, that do not recover to Grade 0-1 within 12 weeks of the last dose.

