Dosing interruptions are permitted in the case of medical / surgical events or logistical reasons not related to study therapy (e.g., elective surgery, unrelated medical events, patient vacation, and/or holidays). Ipilimumab should be permanently discontinued for subject's who fail to complete the full treatment course of ipilimumab within 16 weeks from administration of first dose.

If a subject's study treatment has been interrupted for more than 2 doses of pembrolizumab and/or ipilimumab, the investigator must contact the Principal Investigator to review the subject's condition in order to resume the treatment. Subjects being treated on combination therapy with pembrolizumab plus ipilimumab who require discontinuation of ipilimumab due to toxicity may continue treatment with pembrolizumab after approval from the Principal Investigator. The reason for discontinuation must be recorded.

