5.5.2 Prohibited Concomitant Medications

Subjects are prohibited from receiving the following therapies during the Screening and Treatment Phase (including retreatment for post-complete response relapse) of this trial:

- Antineoplastic systemic chemotherapy or biological therapy
- Immunotherapy not specified in this protocol
- Chemotherapy
- Investigational agents other than pembrolizumab and ipilimumab
- Radiation therapy
 - Note: Radiation therapy to a symptomatic solitary lesion or to the brain may be allowed after discussion between the investigator and Principal Investigator.
- Live vaccines within 30 days prior to the first dose of trial treatment and while participating in the trial. Examples of live vaccines include, but are not limited to, the following: measles, mumps, rubella, varicella/zoster, yellow fever, rabies, BCG, and typhoid vaccine.
- Systemic glucocorticoids for any purpose other than to modulate symptoms from an
 event of clinical interest of suspected immunologic etiology. The use of physiologic
 doses of corticosteroids may be approved after consultation with the Principal
 Investigator.

Subjects who, in the assessment by the investigator, require the use of any of the aforementioned treatments for clinical management should be removed from the trial. Subjects may receive other medications that the investigator deems to be medically necessary.

Local surgery resulting from disease progression is prohibited. However, if indicated for palliative measure and after Principal Investigator approval, local surgery may be permitted after the Week 12 tumor assessment. Subjects who, in the assessment by the investigator, require the use of any of the aforementioned treatments for clinical management should be removed from the trial. Subjects may receive other medications that the investigator deems to be medically necessary.

The Exclusion Criteria describes other medications which are prohibited in this trial.

There are no prohibited therapies during the Post-Treatment Follow-up Phase.

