8.0 TRIAL PROCEDURES

8.1 Trial Procedures

The Trial Flow Chart - Section 6.0 summarizes the trial procedures to be performed at each visit. Individual trial procedures are described in detail below. It may be necessary to perform these procedures at unscheduled time points if deemed clinically necessary by the investigator.

Furthermore, additional evaluations/testing may be deemed necessary by the Principal Investigator for reasons related to subject safety. In some cases, such evaluation/testing may be potentially sensitive in nature (e.g., HIV, Hepatitis C, etc.), and may require that additional informed consent be obtained from the subject.

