8.1.3 Other Procedures

8.1.3.1 Withdrawal/Discontinuation

When a subject discontinues/withdraws prior to trial completion, all applicable activities scheduled for the final trial visit should be performed at the time of discontinuation. Any adverse events which are present at the time of discontinuation/withdrawal should be followed in accordance with the safety requirements outlined in Section 7.2 - Assessing and Recording Adverse Events. Subjects who a) attain a CR or b) complete 24 months of treatment with pembrolizumab may discontinue treatment with the option of restarting treatment if they meet the criteria specified in Section 7.1.4.2. After discontinuing treatment following assessment of CR, these subjects should return to the site for a Safety Follow-up Visit and then proceed to the Follow-Up Period of the study.

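### Scan timing is not fixed for dose holds, and the clock restarts at discontinuation after an early stop, so progression can be dated later in patients with toxicity and early Kaplan-Meier PFS raised

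*Combined protocol and SAP*

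**What the plan says.** **On-treatment scans.** The imaging row of the flow chart (6.1) is marked at screening, cycle 4 and cycle 8, to be repeated beyond cycle 8. The row is labelled "Tumor Imaging (window includes all of cycle following drug administration", and the footnote to cycle 4 is there to "allow for the scan any time after infusion of the 4th dose". Section 5.5.2 uses calendar language: "local surgery may be permitted after the Week 12 tumor assessment".

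**Holds.** Table 3 in 5.2.1.2 discontinues the subject, for most toxicities, if "Toxicity does not resolve within 12 weeks of last dose". The same section stops ipilimumab for patients who "fail to complete the full treatment course of ipilimumab within 16 weeks from administration of first dose".

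**After stopping.** The follow-up column of the flow chart is headed "Every 12 weeks post discon". Section 8.1.4.1 requires radiologic imaging at that interval (±7 days) for patients who stop for a reason other than progression. The imaging row has no mark at the discontinuation visit or in the follow-up column.

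**End of disease follow-up.** Footnote b of 6.1 gives 2 years after drug discontinuation. Section 8.1.4.1 gives 24 months after the last patient is enrolled. Section 5.8 lists patient-level events and no time cap.

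**PFS.** Section 3.2 summarises PFS by RECIST v1.1 and irRC and hypothesises an improvement on historical ipilimumab. The SAP (10.1) estimates PFS by Kaplan-Meier and names no criterion, event date or censoring rule. Section 13.3 calls irRC two-dimensional and specifies single diameters only.

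**The concern.** Radiographic progression is dated when a scan is done. If scans move with doses, or restart their clock at discontinuation, patients with toxicity are scanned later than patients on schedule, and their progression is dated later for that reason alone. The early PFS curve is then too high by an amount that depends on how many patients are held or stop. Two sites could also apply different readings to the same hold.

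The unsettled end of follow-up gives the same patient different imaging durations and censoring. An irRC-based PFS cannot be produced from the one-dimensional measurements that 13.3 specifies.

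**Working it through.** The plan states no numerical PFS figure to reproduce. Its response-rate figures do reproduce: power 0.901 (stated 90%), early-stop probability 0.659 (stated 0.65), attained alpha 0.0977 (limit 0.10), 90% half-width 9.0 points at n = 70. None of them takes scan dates as an input.

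**Scan dates, first dose = day 1.**
- On schedule: dose 4 on day 64, cycle to day 84; dose 8 on day 148, cycle to day 168. Scans fall in about weeks 9-12 and 21-24.
- Early stop when dose 2, 3 or 4 is due: day 22, 43 or 64, plus 84 = day 106, 127 or 148, about week 15, 18 or 21. This applies under either reading of holds.
- Hold, dose-based reading: dose 4 at the 16-week limit is day 113, so the first scan is due by day 133 (week 19). A 12-week gap after dose 3 puts the next dose on day 43 + 84 = 127, with the scan due by day 147 (week 21). That dose falls after the 16-week ipilimumab limit.

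**Effect on PFS.** Inputs: exponential progression with latent median m. One value, 2.86 months, is the historical ipilimumab time to progression in 4.1.1; 2.0 and 5.0 months are assumptions. First scan is uniform over days 64-85, then every 84 days, with progression dated at the next scan. With λ = ln 2/(30.4375 m), on-schedule PFS at day 91 is

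A = (e^(−64λ) − e^(−85λ))/(21λ).

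A patient not yet scanned by day 91 counts as progression-free, so a share p of such patients raises PFS by p(1 − A). If half of progression is found off schedule, the rise is half of that.

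| Latent median (months) | A | 10% held 6 weeks: 0.10(1 − A) | half off schedule | 13.6% stop before dose 4: 0.136(1 − A) | half off schedule |
|---|---|---|---|---|---|
| 2.0 | 0.429 | +5.7 | +2.9 | +7.8 | +3.9 |
| 2.86 | 0.553 | +4.5 | +2.2 | +6.1 | +3.0 |
| 5.0 | 0.713 | +2.9 | +1.4 | +3.9 | +2.0 |

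Values are percentage points at week 13. The 10% and 6 weeks are assumed. The 13.6% is the share stopping both drugs (3 patients) in the phase I study of the same combination cited in 4.2.2. The timing of those stops is not given, so placing them all before dose 4 is an upper-end assumption.

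**Later times, 10% held 6 weeks.** Let r = e^(−42λ). By day 127 all held patients have been scanned once, later than the others, and the difference is 0.10·A(r − 1) = −1.6, −1.6 and −1.2 points for m = 2.0, 2.86 and 5.0. At 6 months it is 0.10·A(r − r²) = +1.0, +1.1 and +1.0. For the early stops, the 6-month difference is 0.136 × (mean of e^(−106λ), e^(−127λ), e^(−148λ) − A·r²) = +1.0, +1.1 and +1.0.

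One case does not fade. On the dose-based reading, a 12-week hold after dose 1, 2 or 3 that ends in discontinuation puts the next mandated scan at day 169, 190 or 211. An assumed 5% of such patients leaves PFS 2.8 to 2.3 points high at 6 months for m = 2.0 to 2.86.

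For scale, a 95% half-width near 50% at n = 70 is 1.96·√(0.25/70) = 11.7 points.

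**End of follow-up.** At 3 patients per month (10.2), accrual takes 70/3 = 23.3 months. A first-enrolled patient stopping at month 3 is followed to 3 + 24 = month 27 under footnote b and to 23.3 + 24 = month 47.3 under 8.1.4.1. A last-enrolled patient completing 24 months of treatment has 24 further months under footnote b and none under 8.1.4.1. The trial would run to 47.3 months under 8.1.4.1 and up to 23.3 + 24 + 24 = 71.3 months (5.9 years) under footnote b. The trial summary gives 4 years.

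**The case against.** A reader might infer that the plan has no calendar rule for early stops. It has one, in 8.1.4.1; the problem is only that it counts from discontinuation and no scan is marked at that visit.

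A reader might also treat the hold bias as certain. It needs the dose-based reading. The Week 12 wording in 5.5.2 points to calendar intent, and the cycle 4 footnote may be a deliberate choice to image after four doses. What stands is an ambiguity that sites can resolve in two ways.

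The plan has safeguards. Section 8.1 says "It may be necessary to perform these procedures at unscheduled time points if deemed clinically necessary by the investigator", 8.1.3.1 asks that "all applicable activities scheduled for the final trial visit should be performed at the time of discontinuation", and 5.2.1.2 requires Principal Investigator review before resuming after more than two missed doses. These make off-schedule detection more likely, which is why the halved figures matter. None of them mandates a scan: the first is discretionary, the second refers to a visit at which no imaging is marked, and the third concerns resuming treatment.

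The size rests on assumed rates, and most effects lie inside the 11.7-point half-width. That is fair, but an interval describes sampling error and does not cover a shift in scan dates.

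Three incompatible ends of follow-up would be too strong a reading. Section 5.8 lists patient-level events without denying a study-level end, so the firm conflict is footnote b against 8.1.4.1. RECIST v1.1 in 3.2 is likewise not contradicted; only irRC is.

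**Conclusion.** The concern holds as an ambiguity about holds and a late clock after early stops. Both delay the dating of progression in patients with toxicity and raise early PFS: about 3 to 6 points at week 13 per 10% of patients held 6 weeks, and about 4 to 8 points if 13.6% stop before dose 4, for latent medians of 5.0 down to 2.0 months. Finding half of progression off schedule halves these. The hold effect can reverse near day 127, and both effects are about 1 point by 6 months, apart from stops after a failed hold. The figures assume exponential progression and hold and stop rates that the documents do not supply.

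PFS is a secondary, descriptive endpoint, and the stated response-rate design figures are unchanged. It is tempting to go further and say that late scans would carry the observed median past 2.86 months and produce a false gain over ipilimumab. The documents do not support that: 2.86 months is a time to progression, and the scan schedule behind it is not given.

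The conflicts over the end of follow-up, the unmarked follow-up imaging and irRC are in the text and need no assumptions.

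**What to change.** 1. State that tumor imaging is counted from first dose within the existing windows (about weeks 9-12 and 21-24, allowing for the ±3-day dosing window, then every 12 weeks), regardless of holds or early stops, until progression or another end listed in 8.1.4.1. Reconcile this with Week 12 in 5.5.2.
2. Mark follow-up imaging in the flow chart, and use one end of disease follow-up in footnote b, 8.1.4.1 and 5.8, consistent with the 4-year trial duration.
3. Reconcile the PFS criterion in 3.2 with 13.3: either name irRECIST in place of irRC, or add two-dimensional measurement if irRC is meant.
4. State in the SAP that PFS is descriptive, and that 2.86 months is a time-to-progression figure whose scan schedule is not given.

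The cost is mainly wording. Some scans will fall at non-dosing visits. Early stoppers are scanned 106 − 84 = 22 to 148 − 64 = 84 days sooner than now, and some will have an extra scan. Held patients will have their first response assessment after fewer than four doses, which also affects the timing of the primary assessment and should be accepted knowingly. The change removes the difference between patients on and off schedule. It does not remove the ordinary upward effect of dating progression at scans (at a latent median of 2.86 months, 55% on schedule against a true 48% at week 13), and it does not supply the event-date and censoring rules that the SAP lacks.
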